1 GLOSSARY OF TERMS

Names of Test Product(s)	Throughout this document, test product(s) will be referred to as [REDACTED] soft contact lenses or [REDACTED] contact lenses [REDACTED]
Name of Control Product(s)	CooperVision® BIOFINITY® soft contact lenses (Biofinity contact lenses or Biofinity)
Adverse Device Effect (ADE)	Adverse event related to the use of an investigational medical device (test product) or control product. Note: This definition includes adverse events resulting from insufficient or inadequate instructions for use, deployment, implantation, installation, or operation; any malfunction; and use error or intentional misuse of the test product or control product.
Adverse Event (AE)	Any untoward medical occurrence, unintended disease or injury, or untoward clinical signs (including abnormal laboratory findings) in subjects, users or other persons, whether or not related to the investigational medical device (test product). Note: For subjects, this definition includes events related to the test product, the control product, or the procedures involved. For users or other persons, this definition is restricted to events related to the test product. Requirements for reporting Adverse Events in the study can be found in Section 11.
Anticipated Serious Adverse Device Effect	Serious adverse device effect which by its nature, incidence, severity, or outcome has been identified in the risk management file.
Device Deficiency	Inadequacy of a medical device with respect to its identity, quality, durability, reliability, safety, or performance. Note: This definition includes malfunctions, use errors, and inadequate labeling.

	Requirements for reporting Device Deficiencies in the study can be found in Section 11.
Enrolled Subject	Any subject who signs an informed consent form for participation in the study.
Interventional Clinical Trial	A research trial that prospectively assigns, whether randomly or not, human participants or groups of humans to one or more health-related interventions to evaluate the effects on health outcomes, and/or a research trial in which diagnostic or monitoring procedures beyond standard of care are conducted and generate outcomes for use in analysis of data.
Investigational Product	Is defined as a preventative (vaccine), a therapeutic (drug or biologic), device, diagnostic, or palliative used as a test or control product in a clinical trial, including a product with a marketing authorization when used or assembled (formulated or packaged) in a way different from the authorized form, or when used for an unauthorized indication, or when used to gain further information about the authorized form.
Malfunction	Failure of a medical device to perform in accordance with its intended purpose when used in accordance with the instructions for use or clinical investigation plan.
Non-serious Adverse Event	Adverse event that does not meet the criteria for a serious adverse event.
Randomized Subjects	Any subject who is assigned a randomized treatment.
Serious Adverse Device Effect (SADE)	Adverse device effect that has resulted in any of the consequences characteristic of a serious adverse event.
Serious Adverse Event (SAE)	Adverse event that led to any of the following: 
 • Death.

	
• A serious deterioration in the health of the subject that either resulted in:
a. a life-threatening illness or injury. Note: Life-threatening means that the individual was at immediate risk of death from the event as it occurred, ie, it does not include an event which hypothetically might have caused death had it occurred in a more severe form.b. any potentially sight-threatening event or permanent impairment to a body structure or a body function.c. in-patient hospitalization or prolonged hospitalization. Note: Planned hospitalization for a pre-existing condition, without serious deterioration in health, is not considered a serious adverse event. In general, hospitalization signifies that the individual remained at the hospital or emergency ward for observation and/or treatment (usually involving an overnight stay) that would not have been appropriate in the physician's office or an out-patient setting. Complications that occur during hospitalization are adverse events. If a complication prolongs hospitalization or fulfills any other serious criteria, the event is serious. When in doubt as to whether "hospitalization" occurred, the event should be considered serious.d. a medical or surgical intervention to prevent a) or b).e. any indirect harm as a consequence of incorrect diagnostic test results when used within manufacturer's instructions for use.
--	---

	
 • Fetal distress, fetal death, or a congenital abnormality or birth defect. 
Refer to Section 11 for additional SAEs.

Significant Non-Serious Adverse Event
	
Is a symptomatic, device-related, non-sight threatening adverse event that warrants discontinuation of any contact lens wear for greater than or equal to 2 weeks.
 
Refer to Section 11 for additional Significant Non-Serious AEs.

Unanticipated Serious Adverse Device Effect
	
Serious adverse device effect which by its nature, incidence, severity, or outcome has not been identified in the risk management file.

Use Error
	
Act or omission of an act that results in a different medical device response than intended by manufacturer or expected by user. Note: This definition includes slips, lapses, and mistakes. An unexpected physiological response of the subject does not in itself constitute a use error.

2 LIST OF ACRONYMS AND ABBREVIATIONS

Table 2-1 List of Acronyms and Abbreviations Used in This Protocol

Abbreviation	Definition
ADE	Adverse device effect
AE	Adverse event
BCVA	Best corrected visual acuity
Biofinity contact lens, Biofinity soft contact lens, or Biofinity	CooperVision BIOFINITY (comfilcon A) soft contact lenses
CFR	Code of Federal Regulations
CLEAR CARE	CLEAR CARE Cleaning & Disinfecting Solution
COL	Clinical operations lead
CRF	Case report form
CSM	Clinical site manager
CTT	Clinical trial team
D	Diopter(s)
D/C	Discontinue
eCRF	Electronic case report form
EDC	Electronic data capture
FDA	US Food and Drug Administration
GCP	Good Clinical Practice
IB	Investigator's brochure
ICF	Informed consent form
ICH	International Council for Harmonisation of Technical Requirements for Pharmaceuticals for Human Use
IEC	Independent ethics committee
IP	Investigational product
IRB	Institutional review board
IRT	Interactive response technology
ISO	International Organization for Standardization
██████████	██████████
LID	Lens identification
logMAR	Logarithm of the minimum angle of resolution
mm	Millimeter
MOP	Manual of procedures
N/A	Not applicable
██████████ contact lens or ██████████	██████████ soft contact lenses
OD	Right eye
OS	Left eye
OU	Both eyes
██████████	██████████

Abbreviation	Definition
SAE	Serious adverse event
SADE	Serious adverse device effect
SiHy	Silicone hydrogel
SOP	Standard operating procedure
[REDACTED]	[REDACTED]
US/USA	United States of America
USAN	United States Adopted Name
USV	Unscheduled visit
VA	Visual acuity
vs	Versus

3 PROTOCOL SUMMARY

This will be a prospective, randomized, [REDACTED] controlled, double-masked, parallel-group daily wear clinical study.

Approximately 8 sites in the US will enroll approximately 120 subjects. Subjects will be expected to attend 6 office visits: Screening/Baseline/Dispense, Week 1 Follow-up, Week 2 Follow-up, Month 1 Follow-up, Month 2 Follow-up, and Month 3 Follow-up/Exit. The total expected duration of participation for each subject is approximately 3 months in this daily wear clinical study. Approximately 80 subjects will be assigned to wear the test lenses and 40 subjects will be assigned to wear the control lenses, following the 2:1 subject allocation ratio as recommended by ISO 11980:2012 and the US FDA 510(k) guidance document.

Subjects and the study personnel conducting the study evaluations will be masked to treatment. Subjects who meet the inclusion and exclusion criteria will be randomized to wear either the test contact lenses [REDACTED] in both eyes or the control contact lenses (Biofinity) in both eyes for 3 months of daily wear exposure. Following randomization, subjects will be trial fit in the assigned study lens using the fitting set supplied by the Sponsor, and the overall fit and correct contact lens power for each eye will be determined. [REDACTED]

[REDACTED]
[REDACTED]
[REDACTED]
[REDACTED]

The delegated [REDACTED] staff member will then complete a contact lens order form to obtain lenses for each subject. The Sponsor will send investigational products for each subject to the site after receiving an order from the Investigator.

At the Screening/Baseline/Dispense Visit, study lenses will be dispensed to qualified subjects and the subject will be provided with sufficient lens supplies to follow a monthly replacement schedule until the next visit. All study lenses will be worn for at least 5 days per week and 8 hours per day in a daily wear modality (eg, will not be worn while sleeping). [REDACTED]

[REDACTED]
[REDACTED]

Problem lenses (if any) will not be discarded, but collected by the subject and returned to the investigational site. Regardless of whether the subject is randomized to the test or the control group, CLEAR CARE® Cleaning & Disinfecting Solution (CLEAR CARE) must be used for cleaning and disinfection. [REDACTED]

[REDACTED]
[REDACTED]

[Redacted]

[Redacted]

Visual acuity with study lenses will be measured at all visits, and any decrease of 2 or more lines from the Screening/Baseline/Dispense Visit to any follow-up visit should be explained by the Investigator. [Redacted]

[Redacted]

Investigational Product Type	Medical Device
Study Type	Interventional
Investigational Products	Test Product: [Redacted] soft contact lens Control Product: Biofinity soft contact lens
Purpose and Rationale	The purpose of this clinical study is to evaluate the performance of the investigational [Redacted] soft contact lens compared to the commercially available Biofinity soft contact lens when worn in a daily wear modality, by assessing visual acuity as the primary variable. The overall objective is to evaluate safety and effectiveness of the [Redacted] soft contact lens when worn for daily wear and replaced monthly as compared to Biofinity soft contact lens.
Objective(s)	The primary objective is to evaluate visual acuity of the investigational [Redacted] soft contact lens compared to the commercially available Biofinity soft contact lens.
Endpoint(s)	Primary Effectiveness 
 Distance VA (Snellen) with study lenses [Redacted] [Redacted] [Redacted]

	
█ [REDACTED]█ [REDACTED]█ [REDACTED]█ [REDACTED]█ [REDACTED]█ [REDACTED]█ [REDACTED]█ [REDACTED]█ [REDACTED]█ [REDACTED]█ [REDACTED]█ [REDACTED] 
Safety
 
• AEs• Biomicroscopy findings• Device deficiencies

Assessment(s)
	
Effectiveness
 
• VA with study lenses (Snellen distance)• VA with habitual correction (Snellen distance)• Manifest refraction• BCVA (Snellen distance with manifest refraction) 
█ [REDACTED]
█ [REDACTED]█ [REDACTED]█ [REDACTED]
█ [REDACTED]█ [REDACTED]█ [REDACTED]█ [REDACTED]

	
 █ [REDACTED] █ [REDACTED] █ [REDACTED] 
█ [REDACTED] 
█ [REDACTED] 
█ [REDACTED] 
█ [REDACTED] 
█ [REDACTED] █ [REDACTED] █ [REDACTED] • Discontinuations with reason 
Safety
 
 • AEs • Biomicroscopy • Device deficiencies
Study Design	
This will be a prospective, randomized, [REDACTED] [REDACTED] controlled, double-masked, parallel-group, daily wear clinical study. Subject participation in the study will be approximately 14 weeks with approximately 3 months of exposure to study lenses.

Subject Population	
Volunteer subjects aged 18 or over who are adapted daily wear frequent replacement soft contact lens wearers, excluding Biofinity habitual wearers, have at least 3 months of soft contact lens wearing experience, and who wear their habitual lenses at least 5 days per week and at least 8 hours per day.
 
Subjects must require contact lens correction in a sphere power range from -1.00 to -6.00 D. [REDACTED]
 
[REDACTED]
 
[REDACTED]
 
[REDACTED]

Table 3–1 Schedule of Study Procedures and Assessments

Procedure/ Assessment	Visit 1 Screening/ Baseline/ Dispense	Visit 2 Week 1 Follow-up ⁵	Visit 3 Week 2 Follow-up ⁵	Visit 4 Month 1 Follow-up ⁵	Visit 5 Month 2 Follow-up ⁵	Visit 6 Month 3 Follow- up/Exit ⁵	Early Exit	USV
	Day 1	Day 8 (-2/+2 days)	Day 15 (-3/+3 days)	Day 30 (-3/+5 days)	Day 60 (-3/+5 days)	Day 95 (-3/+5 days)		
Informed Consent	X							
Demographics	X							
Medical History	X	X	X	X	X	X	X	(X)
Concomitant Medications	X	X	X	X	X	X	X	(X)
Inclusion/Exclusion	X							
Habitual lens information (brand/manufacturer, power, modality/wear success, habitual lens care brand)	X							
VA w/ habitual correction (OD,OS Snellen distance)	X					X	X	(X)
Manifest refraction ⁴	X	(X)	(X)	(X)	(X)	X	X	(X)
BCVA ⁴ (OD,OS Snellen distance with manifest refraction)	X	(X)	(X)	(X)	(X)	X	X	(X)
[REDACTED]	■					■	■	■
Biomicroscopy	X	X	X	X	X	X	X	(X)

Printed By:

Print Date:

Alcon - Business Use Only Protocol - Clinical
 Document: TDOC-0056910
 Status: Effective
 Version: 2.0; Most-Recent; Effective; CURRENT
 Effective Date: 11/8/2019 11:59:14 AM

Procedure/ Assessment	Visit 1 Screening/ Baseline/ Dispense	Visit 2 Week 1 Follow-up ⁵	Visit 3 Week 2 Follow-up ⁵	Visit 4 Month 1 Follow-up ⁵	Visit 5 Month 2 Follow-up ⁵	Visit 6 Month 3 Follow- up/Exit ⁵	Early Exit	USV
	Day 1	Day 8 (-2/+2 days)	Day 15 (-3/+3 days)	Day 30 (-3/+5 days)	Day 60 (-3/+5 days)	Day 95 (-3/+5 days)		
[REDACTED]	X							
Randomize and record lens power	X							
[REDACTED]	X							
Order study lenses*	X							
IP Dispense*	X	X	(X)	(X)	(X)			(X)
VA w/ study lenses (OD, OS Snellen distance) ¹	X	X	X	X	X	X	X	(X)
[REDACTED]		■	■	■	■	■	■	■
[REDACTED]	■	■	■	■	■	■	■	■
[REDACTED]	■	■	■	■	■	■	■	■

Printed By:

Print Date:

Procedure/ Assessment	Visit 1 Screening/ Baseline/ Dispense	Visit 2 Week 1 Follow-up ⁵	Visit 3 Week 2 Follow-up ⁵	Visit 4 Month 1 Follow-up ⁵	Visit 5 Month 2 Follow-up ⁵	Visit 6 Month 3 Follow- up/Exit ⁵	Early Exit	USV
	Day 1	Day 8 (-2/+2 days)	Day 15 (-3/+3 days)	Day 30 (-3/+5 days)	Day 60 (-3/+5 days)	Day 95 (-3/+5 days)		
[REDACTED]								
[REDACTED]								
[REDACTED]								
[REDACTED]								
[REDACTED]								
[REDACTED]								
[REDACTED]								
AEs	X	X	X	X	X	X	X	(X)
Device deficiencies	X	X	X	X	X	X	X	(X)
Exit Form	(X)	(X)	(X)	(X)	(X)	(X)	X	(X)

Printed By:

Print Date:

[REDACTED] ct.

USV = Unscheduled Visit

*source only

[REDACTED]

⁵All follow-up visits should be scheduled at least 4 hours after lens insertion.

[REDACTED]

[figure not shown]

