8.1 Inclusion Criteria

Written informed consent must be obtained before any study specific assessment is performed. Upon signing informed consent, the subject is considered enrolled in the study.

Subjects eligible for inclusion in this study must fulfill **all** of the following criteria:

1. At least 18 years of age.
2. Able to understand and sign an IRB/IEC approved Informed Consent form.
3. Willing and able to attend all scheduled study visits as required per protocol.
4. Successful wear of spherical daily wear frequent replacement soft contact lenses for distance correction in both eyes during the past 3 months for a minimum of 5 days per week and 8 hours per day.
5. Manifest cylinder ≤ 0.75 D in each eye.
6. Best spectacle corrected (using manifest refraction) VA 20/25 or better in each eye.
7. Requiring contact lens sphere power from -1.00 to -6.00 D and willing to wear assigned study lenses as required per protocol
8. Distortion-free keratometric readings.
9. 
10. Possess and willing to wear habitual spectacles for vision correction when study lenses are not worn, if needed.

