10.5 Discontinued Subjects

10.5.1 Screen Failures

Screen failures are subjects who were excluded from the study after signing the informed consent, not meeting the inclusion/exclusion criteria, and prior to randomization to product/dispense of study product.

The Investigator must document the reason for screen failure in the subject’s case history source documents.

Subject numbers must not be re-used.

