1.2 Study Description

Key components of the study are summarized in Table 1-1.

Table 1-1 Study Description Summary

Study Design	Prospective, multi-center, randomized, [REDACTED] controlled, double-masked, parallel-group
Study Population	
Volunteer subjects aged 18 or over who are adapted daily wear frequent replacement soft contact lens wearers, excluding Biofinity habitual wearers, have at least 3 months of soft contact lens wearing experience, and who wear their habitual lenses at least 5 days per week and at least 8 hours per day.
 
Subjects must require contact lens correction in a sphere power range from -1.00 to -6.00 D. [REDACTED] [REDACTED] [REDACTED]
 
Target to complete: 90 subjects (60:30; Test:Control) Planned to enroll: ~120 subjects

Number of Sites	~8 (US)
Test Product	[REDACTED] soft contact lenses [REDACTED]
Control Product	CooperVision® BIOFINITY® (comfilcon A) soft contact lenses (Biofinity)
Duration of Treatment	Approximately 3 months
Visits	
Visit 1: Screening/Baseline/Dispense (Day 1) Visit 2: Week 1 Follow-up (Day 8 -2/+2 days) Visit 3: Week 2 Follow-up (Day 15 -3/+3 days) Visit 4: Month 1 Follow-up (Day 30 -3/+5 days) Visit 5: Month 2 Follow-up (Day 60 -3/+5 days) Visit 6: Month 3 Follow-up/Exit (Day 95 -3/+5 days)

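### Can about 80 test and 40 control assignments come from about 120 enrolled subjects when enrolled means consented?

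*Protocol*

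**What the plan says.** Protocol section 3 gives the overall size as "Approximately 8 sites in the US will enroll approximately 120 subjects" and then the split: "Approximately 80 subjects will be assigned to wear the test lenses and 40 subjects will be assigned to wear the control lenses". Sections 7.1 and 8 repeat the approximate 120, at about 15 subjects per site. SAP Table 1-1 has "Planned to enroll: ~120 subjects" together with "Target to complete: 90 subjects (60:30; Test:Control".

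The protocol glossary defines an enrolled subject as "Any subject who signs an informed consent form for participation in the study" and a randomized subject as "Any subject who is assigned a randomized treatment". Section 8.1 repeats the first definition: "Upon signing informed consent, the subject is considered enrolled in the study". Section 10.5.1 places the losses between the two: "Screen failures are subjects who were excluded from the study after signing the informed consent", and before randomization. Section 8.3 rules out rescreening.

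The sample size sections (Protocol 12.8, SAP 8) do not derive 120 or 90. They cite guidance minimums: at least 50 evaluable subjects followed for 3 months with a 2:1 ratio, and 50 completed test subjects.

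**The concern.** On the protocol's own definitions, the enrolled count includes people who consent and then fail screening, and the assigned count does not. Both are about 120, so the plan appears to allow for no screen failures. Yet it has a screen-failure section, 17 exclusion criteria, and limits on cylinder, acuity and lens power.

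If recruitment stopped at 120 consents, fewer than 80 and 40 subjects would be randomized. The gap between 120 and the 90 intended completers would then have to cover screen failures as well as discontinuations, and neither document says so. What seems at stake is the 60:30 completion target and, behind it, the number of completed subjects available for the submission.

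**Working it through.** **Inputs.** About 120 enrolled and about 80:40 assigned (Protocol 3). Ratio 2:1 (Protocol 9.3, SAP 1.3). Target of 90 completers, 60:30 (SAP Table 1-1). Cited minimum of 50 completed test subjects (Protocol 12.8, SAP 8). The visible text gives no screen-failure or discontinuation rate, so the screen-failure fraction *s* is assumed over a range. Discontinuation is taken as equal in the two arms.

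**The plan's own figures.** 120 × 2/3 = 80 and 120 × 1/3 = 40. Also 90/(1 − 0.25) = 120, 60/(1 − 0.25) = 80 and 30/(1 − 0.25) = 40. The three sizes therefore fit together with a 25% loss after randomization and no screen failures. The 25% is inferred from 90 of about 120; it is not stated.

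**Reading A: 120 is a cap on consents.**

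- Randomized = 120(1 − *s*), split 2:1.
- Largest discontinuation that still gives 60:30 = 1 − 90/[120(1 − *s*)].
- Largest discontinuation that still gives 50 test completers = 1 − 50/[80(1 − *s*)].

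| Assumed *s* | Randomized | Allowance to 60:30 | Allowance to 50 test |
|---|---|---|---|
| 0% | 80:40 | 25.0% | 37.5% |
| 5% | 76:38 | 21.1% | 34.2% |
| 10% | 72:36 | 16.7% | 30.6% |
| 15% | 68:34 | 11.8% | 26.5% |
| 20% | 64:32 | 6.3% | 21.9% |
| 25% | 60:30 | 0% | 16.7% |

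The test arm falls to 50 randomized, with nothing left for discontinuation, only at *s* = 1 − 50/80 = 37.5%.

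**Reading B: about 80:40 randomized is the planning figure.** The 25% allowance is unchanged and only the number of consents is understated. Consents needed = 120/(1 − *s*), rounded up: 127 at 5%, 134 at 10%, 142 at 15% and 150 at 20%.

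**How much slack the word approximate gives.** Three screen failures among 120 leave 117, or 78:39, which is still about 80:40.

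**What depends on the answer.** Protocol 12.4.1.1 and SAP 4.2 plan no hypothesis for the primary endpoint, and the SAP's executive summary says success criteria do not apply. The analysis sets (Protocol 12.2, SAP 2) are defined by consent, dispensing and completion as they occur. No denominator uses the planned 120.

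**The case for a change.** The strongest case for a change is that the documents define their terms and then do not keep to them. Enrolled means consented in the glossary, in section 8.1 and in the All Enrolled set of both documents, and sections 3, 7.1 and 8 and SAP Table 1-1 all attach 120 to enrolment. A site that applies the definition could stop at its share of 120 consents, while one that looks at 80:40 would carry on. Trial fitting follows randomization, so some randomized subjects may never be dispensed lenses and could not enter the Completed set. That takes up more of the same allowance. On Reading A with 20% screen failure, 60:30 would need discontinuation of 6.3% or less, which is tight.

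The inconsistency of terms stands, and so does the arithmetic. The consequence stands only in part. No visible passage makes 120 consents the point at which recruitment stops; section 8 calls 120 an aim, and section 3 says how many subjects are to be assigned lenses. The bar on rescreening stops the same person returning but does not stop a site consenting someone else. The number of exclusion criteria does not give a failure rate: many are history or status items, and the population is adapted, successful wearers. Finally, 60:30 appears only as a target in a SAP table. The stated basis for the size is 50 completed test subjects, and no consequence is attached to missing 60.

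**Conclusion.** This is loose use of the word enrolled, not an error in the size of the study. The approximate figures of 120 enrolled and 80:40 assigned agree only if screen failures are close to zero. The sensible reading, and the one a trial team would act on, is about 120 randomized. On that reading nothing shrinks and sites simply consent a few more people.

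On the less favourable reading, the implied 25% margin to 60:30 falls to between 21.1% and 6.3% for assumed screen-failure rates of 5% to 20%. Over the same range, the margin to the cited 50 test completers stays between 34.2% and 21.9%. These margins rest on the assumed rates and on equal discontinuation in the two arms.

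Screen failures precede randomization, so they do not disturb the 2:1 assignment or the comparison between lenses. With a purely descriptive analysis there is no power to lose, and a somewhat smaller sample would only make the summaries a little less precise. Clearer wording would change no result or conclusion, so no change to the plan is called for.
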